## 10.2. Appendix 2: Clinical Laboratory Tests

The following safety laboratory tests will be performed at times defined in the [SoA](#) section of this protocol. Additional laboratory results may be reported on these samples as a result of the method of analysis or the type of analyzer used by the clinical laboratory, or as derived from calculated values. These additional tests would not require additional collection of blood. Unscheduled clinical laboratory measurements may be obtained at any time during the study to assess any perceived safety issues.

**Table 1. Protocol-Required Safety Laboratory Assessments**

Hematology	Chemistry	Other
Hemoglobin	BUN and creatinine	At times listed in SOA:
Hematocrit	Calcium	• Pregnancy test ( $\beta$ -hCG) a
RBC count	Sodium	
MCV	Potassium	
MCH	Chloride	
MCHC	Total CO 2 (bicarbonate)	
Platelet count	AST, ALT	
WBC count	Total bilirubin	
Total neutrophils (Abs)	Alkaline phosphatase	
Eosinophils (Abs)	Uric acid	
Monocytes (Abs)	Albumin	
Basophils (Abs)	Total protein	
Lymphocytes (Abs)	Phosphate (non-fasted)	

a. Local urine testing will be standard for the protocol unless serum testing is required by local regulation or IRB/EC. Serum or urine  $\beta$ -hCG for female participants of childbearing potential.

The investigator must review the laboratory report, document this review, and record any clinically relevant changes occurring during the study in the AE section of the CRF.

### 10.3. Appendix 3: Adverse Events: Definitions and Procedures for Recording, Evaluating, Follow-Up, and Reporting

#### 10.3.1. Definition of AE

AE Definition

• An AE is any untoward medical occurrence in a patient or clinical study participant, temporally associated with the use of study intervention, whether or not considered related to the study intervention.

• Note: An AE can therefore be any unfavorable and unintended sign (including an abnormal laboratory finding), symptom, or disease (new or exacerbated) temporally associated with the use of study intervention.

Events Meeting the AE Definition

• Any abnormal laboratory test results (hematology, clinical chemistry, or urinalysis) or other safety assessments (eg, ECG, radiological scans, vital sign measurements), including those that worsen from baseline, considered clinically significant in the medical and scientific judgment of the investigator. Any abnormal laboratory test results that meet any of the conditions below must be recorded as an AE:

• Is associated with accompanying symptoms.

• Requires additional diagnostic testing or medical/surgical intervention.

• Leads to a change in study dosing (outside of any protocol-specified dose adjustments) or discontinuation from the study, significant additional concomitant drug treatment, or other therapy.

• Exacerbation of a chronic or intermittent preexisting condition, including either an increase in frequency and/or intensity of the condition.

• New condition detected or diagnosed after study intervention administration, even though it may have been present before the start of the study.

• Signs, symptoms, or the clinical sequelae of a suspected drug-drug interaction.

• Signs, symptoms, or the clinical sequelae of a suspected overdose of either study intervention or a concomitant medication. Overdose per se will not be reported as an AE or SAE unless it is an intentional overdose taken with possible

suicidal/self-harming intent. Such overdoses should be reported regardless of sequelae.

#### Events **NOT** Meeting the AE Definition

- Any clinically significant abnormal laboratory findings or other abnormal safety assessments that are associated with the underlying disease, unless judged by the investigator to be more severe than expected for the participant's condition.
- The disease/disorder being studied or expected progression, signs, or symptoms of the disease/disorder being studied, unless more severe than expected for the participant's condition.
- Medical or surgical procedure (eg, endoscopy, appendectomy): the condition that leads to the procedure is the AE.
- Situations in which an untoward medical occurrence did not occur (social and/or convenience admission to a hospital).
- Anticipated day-to-day fluctuations of preexisting disease(s) or condition(s) present or detected at the start of the study that do not worsen.

#### 10.3.2. Definition of an SAE

**An SAE is defined as any untoward medical occurrence that, at any dose, meets one or more of the criteria listed below:**

**a. Results in death**

**b. Is life-threatening**

The term "life-threatening" in the definition of "serious" refers to an event in which the participant was at risk of death at the time of the event. It does not refer to an event that hypothetically might have caused death if it were more severe.

**c. Requires inpatient hospitalization or prolongation of existing hospitalization**

In general, hospitalization signifies that the participant has been admitted (usually involving at least an overnight stay) at the hospital or emergency ward for observation and/or treatment that would not have been appropriate in the physician's office or outpatient setting. Complications that occur during hospitalization are AEs. If a complication prolongs hospitalization or fulfills any other serious criteria, the event is

serious. When in doubt as to whether “hospitalization” occurred or was necessary, the AE should be considered serious.

Hospitalization for elective treatment of a preexisting condition that did not worsen from baseline is not considered an AE.

**d. Results in persistent or significant disability/incapacity**

- The term disability means a substantial disruption of a person’s ability to conduct normal life functions.
- This definition is not intended to include experiences of relatively minor medical significance, such as uncomplicated headache, nausea, vomiting, diarrhea, influenza, and accidental trauma (eg, sprained ankle), that may interfere with or prevent everyday life functions but do not constitute a substantial disruption.

**e. Is a congenital anomaly/birth defect**

**f. Is a suspected transmission via a Pfizer product of an infectious agent, pathogenic or non-pathogenic, is considered serious.**

The event may be suspected from clinical symptoms or laboratory findings indicating an infection in a participant exposed to a Pfizer product. The terms “suspected transmission” and “transmission” are considered synonymous. These cases are considered unexpected and handled as serious expedited cases by pharmacovigilance personnel. Such cases are also considered for reporting as product defects, if appropriate.

**g. Other situations:**

- Medical or scientific judgment should be exercised by the investigator in deciding whether SAE reporting is appropriate in other situations, such as significant medical events that may jeopardize the participant or may require medical or surgical intervention to prevent one of the other outcomes listed in the above definition. These events should usually be considered serious.
- Examples of such events include invasive or malignant cancers, intensive treatment in an emergency room or at home for allergic bronchospasm, blood dyscrasias or convulsions that do not result in hospitalization, or development of drug dependency or drug abuse.

### 10.3.3. Recording/Reporting and Follow-Up of AEs and/or SAEs During the Active Collection Period

AE and SAE Recording/Reporting		

The table below summarizes the requirements for recording AEs on the CRF and for reporting SAEs on the CT SAE Report Form to Pfizer Safety throughout the active collection period. These requirements are delineated for 3 types of events: (1) SAEs; (2) nonserious AEs; and (3) exposure to the study intervention under study during pregnancy or breastfeeding, and occupational exposure.
 
It should be noted that the CT SAE Report Form for reporting of SAE information is not the same as the AE page of the CRF. When the same data are collected, the forms must be completed in a consistent manner. AEs should be recorded using concise medical terminology and the same AE term should be used on both the CRF and the CT SAE Report Form for reporting of SAE information.
		
Safety Event	Recorded on the CRF	Reported on the CT SAE Report Form to Pfizer Safety Within 24 Hours of Awareness
SAE	All	All
Nonserious AE	All	None
Exposure to the study intervention under study during pregnancy or breastfeeding,	All AEs or SAEs associated with exposure during pregnancy or breastfeeding  Note: Instances of EDP or EDB not associated with an AE or SAE are not captured in the CRF.	All instances of EDP are reported (whether or not there is an associated SAE)*  All instances of EDB are reported (whether or not there is an associated SAE). **
Environmental or occupational exposure to the product under study to a non-participant (not involving EDP or EDB).	None. Exposure to a study non-participant is not collected on the CRF.	The exposure (whether or not there is an associated AE or SAE) must be reported.***

- \* **EDP** (with or without an associated AE or SAE): any pregnancy information is reported to Pfizer Safety using CT SAE Report Form and EDP Supplemental Form; if the EDP is associated with an SAE, then the SAE is reported to Pfizer Safety using the CT SAE Report Form.
- \*\* **EDB** is reported to Pfizer Safety using the CT SAE Report Form which would also include details of any SAE that might be associated with the EDB.
- \*\*\* **Environmental or Occupational exposure:** AEs or SAEs associated with occupational exposure are reported to Pfizer Safety using the CT SAE Report Form.

- When an AE or SAE occurs, it is the responsibility of the investigator to review all documentation (eg, hospital progress notes, laboratory reports, and diagnostic reports) related to the event.
- The investigator will then record all relevant AE or SAE information in the CRF.
- It is **not** acceptable for the investigator to send photocopies of the participant's medical records to Pfizer Safety in lieu of completion of the CT SAE Report Form/AE or SAE CRF page.
- There may be instances when copies of medical records for certain cases are requested by Pfizer Safety. In this case, all participant identifiers, with the exception of the participant number, will be redacted on the copies of the medical records before submission to Pfizer Safety.
- The investigator will attempt to establish a diagnosis of the event based on signs, symptoms, and/or other clinical information. Whenever possible, the diagnosis (not the individual signs/symptoms) will be documented as the AE or SAE.

### Assessment of Intensity

The investigator will make an assessment of intensity for each AE and SAE reported during the study and assign it to 1 of the following categories:

- **Mild:** Asymptomatic or mild symptoms; clinical or diagnostic observations only; intervention not indicated.
- **Moderate:** Minimal, local or noninvasive intervention indicated; limiting age-appropriate instrumental ADL. Instrumental ADL refers to preparing meals, shopping for groceries or clothes, using the telephone, managing money, etc.
- **Severe:** Severe or medically significant but not immediately life-threatening; hospitalization or prolongation of hospitalization indicated; disabling, limiting self care ADL. Self care ADL refers to bathing, dressing and undressing, feeding self, using the toilet, taking medications, and not bedridden.

An event is defined as “serious” when it meets at least 1 of the predefined outcomes as described in the definition of an SAE, NOT when it is rated as severe.

### Assessment of Causality

- The investigator is obligated to assess the relationship between study intervention and each occurrence of each AE or SAE. The investigator will use clinical judgment to determine the relationship.
- A “reasonable possibility” of a relationship conveys that there are facts, evidence, and/or arguments to suggest a causal relationship, rather than a relationship cannot be ruled out.
- Alternative causes, such as underlying disease(s), concomitant therapy, and other risk factors, as well as the temporal relationship of the event to study intervention administration, will be considered and investigated.
- The investigator will also consult the IB and/or product information, for marketed products, in his/her assessment.
- For each AE or SAE, the investigator **must** document in the medical notes that he/she has reviewed the AE or SAE and has provided an assessment of causality.
- There may be situations in which an SAE has occurred and the investigator has minimal information to include in the initial report to the sponsor. However, **it is very important that the investigator always make an assessment of causality for every event before the initial transmission of the SAE data to the sponsor.**
- The investigator may change his/her opinion of causality in light of follow-up information and send an SAE follow-up report with the updated causality assessment.
- The causality assessment is one of the criteria used when determining regulatory reporting requirements.
- If the investigator does not know whether or not the study intervention caused the event, then the event will be handled as “related to study intervention” for reporting purposes, as defined by the sponsor. In addition, if the investigator determines that an SAE is associated with study procedures, the investigator must record this causal relationship in the source documents and CRF, and report such an assessment in the dedicated section of the CT SAE Report Form and in accordance with the SAE reporting requirements.

### **Follow-Up of AEs and SAEs**

- The investigator is obligated to perform or arrange for the conduct of supplemental measurements and/or evaluations, as medically indicated or as requested by the sponsor, to elucidate the nature and/or causality of the AE or SAE as fully as possible. This may include additional laboratory tests or investigations, histopathological examinations, or consultation with other healthcare providers.
- If a participant dies during participation in the study or during a recognized follow-up period, the investigator will provide Pfizer Safety with a copy of any postmortem findings, including histopathology.
- New or updated information will be recorded in the originally submitted documents.
- The investigator will submit any updated SAE data to the sponsor within 24 hours of receipt of the information.

### **10.3.4. Reporting of SAEs**

#### **SAE Reporting to Pfizer Safety via CT SAE Report Form**

- Facsimile transmission of the CT SAE Report Form is the preferred method to transmit this information to Pfizer Safety.
- In circumstances when the facsimile is not working, notification by telephone is acceptable with a copy of the CT SAE Report Form sent by overnight mail or courier service.
- Initial notification via telephone does not replace the need for the investigator to complete and sign the CT SAE Report Form pages within the designated reporting time frames.

## **10.4. Appendix 4: Contraceptive and Barrier Guidance**

### **10.4.1. Male Participant Reproductive Inclusion Criteria**

Male participants are eligible to participate if they agree to the following requirements during the intervention period and for at least 111 days after the last dose of study intervention, which corresponds to the 21 days time needed to eliminate reproductive safety risk of the study intervention(s) *plus* an additional 90 days (a spermatogenesis cycle):

- Be abstinent from heterosexual intercourse as their preferred and usual lifestyle (abstinent on a long term and persistent basis) and agree to remain abstinent.

### **10.4.2. Female Participant Reproductive Inclusion Criteria**

The requirement for participants to be Tanner Stage 1 at enrollment will preclude WOCBP from enrolling, however it is possible participants may become WOCBP later in the study.

A female participant is eligible to participate if she is not pregnant or breastfeeding, and at least 1 of the following conditions applies:

- Is not a WOCBP (see definitions below in [Section 10.4.3](#)).

OR

- Is a WOCBP and agrees to total abstinence until 28 days after the last dose of study intervention, which corresponds to the time needed to eliminate any reproductive safety risk of the study intervention(s). The investigator, or his or her designee, in consultation with the participant and the participant's legally authorized representative, will confirm that the participant has been informed of the potential risks of pregnancy whilst receiving study intervention and advised of the need for continuing total abstinence from sexual activity.

### **10.4.3. Woman of Childbearing Potential**

A woman is considered fertile following menarche and until becoming postmenopausal unless permanently sterile (see below).

If fertility is unclear (eg, amenorrhea in adolescents or athletes) and a menstrual cycle cannot be confirmed before the first dose of study intervention, additional evaluation should be considered.

Women in the following categories are not considered WOCBP:

1. Premenarchal.
2. Premenopausal female with 1 of the following:
  - Documented hysterectomy;

- Documented bilateral salpingectomy;
- Documented bilateral oophorectomy.

For individuals with permanent infertility due to an alternate medical cause other than the above, (eg, mullerian agenesis, androgen insensitivity), investigator discretion should be applied to determining study entry.

Note: Documentation for any of the above categories can come from the site personnel's review of the participant's medical records, medical examination, or medical history interview. The method of documentation should be recorded in the participant's medical record for the study.

#### **10.4.4. Contraception Methods**

Sexual abstinence:

- Sexual abstinence is considered a highly effective method only if defined as refraining from heterosexual intercourse during the entire period of risk associated with the study intervention. The reliability of sexual abstinence needs to be evaluated in relation to the duration of the study and the preferred and usual lifestyle of the participant.

## 10.5. Appendix 5: Liver Safety: Suggested Actions and Follow-Up Assessments

### Potential Cases of Drug-Induced Liver Injury

Humans exposed to a drug who show no sign of liver injury (as determined by elevations in transaminases) are termed “tolerators,” while those who show transient liver injury but adapt are termed “adaptors.” In some participants, transaminase elevations are a harbinger of a more serious potential outcome. These participants fail to adapt and therefore are “susceptible” to progressive and serious liver injury, commonly referred to as DILI. Participants who experience a transaminase elevation above  $3 \times \text{ULN}$  should be monitored more frequently to determine if they are “adaptors” or are “susceptible.”

In the majority of DILI cases, elevations in AST and/or ALT precede TBili elevations ( $>2 \times \text{ULN}$ ) by several days or weeks. The increase in TBili typically occurs while AST/ALT is/are still elevated above  $3 \times \text{ULN}$  (ie, AST/ALT and TBili values will be elevated within the same laboratory sample). In rare instances, by the time TBili elevations are detected, AST/ALT values might have decreased. This occurrence is still regarded as a potential DILI. Therefore, abnormal elevations in either AST OR ALT in addition to TBili that meet the criteria outlined below are considered potential DILI (assessed per Hy’s law criteria) cases and should always be considered important medical events, even before all other possible causes of liver injury have been excluded.

The threshold of laboratory abnormalities for a potential DILI case depends on the participant’s individual baseline values and underlying conditions. Participants who present with the following laboratory abnormalities should be evaluated further as potential DILI (Hy’s law) cases to definitively determine the etiology of the abnormal laboratory values:

- Participants with AST/ALT and TBili baseline values within the normal range who subsequently present with AST OR ALT values  $>3 \times \text{ULN}$  AND a TBili value  $>2 \times \text{ULN}$  with no evidence of hemolysis and an alkaline phosphatase value  $<2 \times \text{ULN}$  or not available.
- For participants with baseline AST **OR** ALT **OR** TBili values above the ULN, the following threshold values are used in the definition mentioned above, as needed, depending on which values are above the ULN at baseline:
  - Preexisting AST or ALT baseline values above the normal range: AST or ALT values  $>2$  times the baseline values AND  $>3 \times \text{ULN}$ ; or  $>8 \times \text{ULN}$  (whichever is smaller).
  - Preexisting values of TBili above the normal range: TBili level increased from baseline value by an amount of at least  $1 \times \text{ULN}$  **or** if the value reaches  $>3 \times \text{ULN}$  (whichever is smaller).

Rises in AST/ALT and TBili separated by more than a few weeks should be assessed individually based on clinical judgment; any case where uncertainty remains as to whether it represents a potential Hy's law case should be reviewed with the sponsor.

The participant should return to the investigator site and be evaluated as soon as possible, preferably within 48 hours from awareness of the abnormal results. This evaluation should include laboratory tests, detailed history, and physical assessment.

In addition to repeating measurements of AST and ALT and TBili for suspected Hy's law cases, additional laboratory tests should include albumin, CK, direct and indirect bilirubin, GGT, PT/INR, total bile acids, and alkaline phosphatase. Consideration should also be given to drawing a separate tube of clotted blood and an anticoagulated tube of blood for further testing, as needed, for further contemporaneous analyses at the time of the recognized initial abnormalities to determine etiology. A detailed history, including relevant information, such as review of ethanol, acetaminophen/paracetamol (either by itself or as a coformulated product in prescription or over-the-counter medications), recreational drug, or supplement (herbal) use and consumption, family history, sexual history, travel history, history of contact with a jaundiced person, surgery, blood transfusion, history of liver or allergic disease, and potential occupational exposure to chemicals, should be collected. Further testing for acute hepatitis A, B, C, D, and E infection, liver imaging (eg, biliary tract), and collection of serum samples for acetaminophen/paracetamol drug and/or protein adduct levels may be warranted.

All cases demonstrated on repeat testing as meeting the laboratory criteria of AST/ALT and TBili elevation defined above should be considered potential DILI (Hy's law) cases if no other reason for the LFT abnormalities has yet been found. **Such potential DILI (Hy's law) cases are to be reported as SAEs, irrespective of availability of all the results of the investigations performed to determine etiology of the LFT abnormalities.**

A potential DILI (Hy's law) case becomes a confirmed case only after all results of reasonable investigations have been received and have excluded an alternative etiology.

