**Overall Design**

**Brief Summary**

This is a Phase 2 open label extension study to assess long-term safety, tolerability, PK, and efficacy of recifercept. The study will be offered to approximately 63 participants from the Phase 2 C4181005 study will be offered to participate who, in the opinion of the investigator, continue to have a positive risk: benefit profile. All enrolled participants will continue treatment with recifercept on 1 of 3 doses (1mg/kg QW, 2 mg/kg BIW, 1.5 mg/kg QD) for up to 24 months. Participants will be children diagnosed with achondroplasia aged  $\geq 15$  months to  $\leq 12$  years (inclusive); who have completed the C4181005 Phase 2 protocol.

Participants will continue to receive recifercept at the dose previously received in the Phase 2 study or at the therapeutic dose once this is identified.

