## 1.2. Schema

### 1.3. Schedule of Activities

The SoA table provides an overview of the protocol visits and procedures. Refer to the [STUDY ASSESSMENTS AND PROCEDURES](#) section of the protocol for detailed information on each procedure and assessment required for compliance with the protocol.

The investigator may schedule visits (unplanned visits) in addition to those listed in the SoA table, in order to conduct evaluations or assessments required to protect the well-being of the participant.

	Enrollment	M1 b	M2 b	M3	M4 b	M5 b	M6	M7 b	M8 b	M9	M10 b	M11 b	M12	M13 b	M14 b	M15	M16 b	M17 b	M18	M19 b	M20 b	M21	M22 b	M23 b	M24	Early Term/Discon.	Follow-up	
Visit Identifier	1	2	3	4	5	6	7	8	9	10	11	12	13	14	15	16	17	18	19	20	21	22	23	24	25	26	27	
Days Relative to Day 1 a	1	29	61	91	121	151	181	211	241	271	301	331	361	391	421	451	481	511	541	571	601	631	661	691	721			
Visit Window (Days)	±7	±7	±7	±7	±7	±7	±7	±7	±7	±7	±7	±7	±7	±7	±7	±7	±7	±7	±7	±7	±7	±7	±7	±7	±7	±7	±7	
Informed consent/assent	X																											
Demography c	X																											
Medical history	X																											
Pregnancy test c	X	X	X	X	X	X	X	X	X	X	X	X	X	X	X	X	X	X	X	X	X	X	X	X	X	X	X	
Contraception check c	X	X	X	X	X	X	X	X	X	X	X	X	X	X	X	X	X	X	X	X	X	X	X	X	X	X	X	
Inclusion/Exclusion Check	X																											
Randomisation	X																											
Physical examination d				X			X			X			X			X			X			X			X	X		
Neurological examination				X			X			X			X			X			X			X			X	X		
Weight				X			X			X			X			X			X			X			X	X		
Vital signs				X			X			X			X			X			X			X			X	X		
Hematology				X			X			X			X			X			X			X			X	X		
Blood chemistry				X			X			X			X			X			X			X			X	X		
Study intervention dispensing	X	X	X	X	X	X	X	X	X	X	X	X	X	X	X	X	X	X	X	X	X	X	X	X	X	X		
Study intervention administration	X	→	→	→	→	→	→	→	→	→	→	→	→	→	→	→	→	→	→	→	→	→	→	→	→			
Dosing diary	X	→	→	→	→	→	→	→	→	→	→	→	→	→	→	→	→	→	→	→	→	→	→	→	→			
Anthropometry				X			X			X			X			X			X			X			X	X		

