#### **4.3. Justification for Dose**

All participants will continue to receive 1 of 3 doses of recifercept (1 mg/kg QW, 2 mg/kg BIW or 1.5 mg/kg QD) as assigned in C4181005 study or at the therapeutic dose once this is identified. Dose will be adjusted according to weight every 3 months.

PK will be assessed on an ongoing basis using sparse sampling approach to inform and update the PopPK model.

Weight limits for this study ([Section 5.2](#)) are based on technical feasibility of dosing with the current study intervention formulation such that injection volumes will be between 0.2 mL and 1 mL.

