2.4. Baseline Variables

The following baseline variables will be summarized for each treatment group (per [Section 3](#)). Details of summary analyses are described in [Section 5.5.1](#).

Demographic characteristics:

- Baseline age
- Gender (female vs. male);
- Race (white, black, Asian, other);
- Baseline body weight;
- Baseline height (cm);
- Baseline Body Mass.

The baseline data measured at Day 1 are:

- Vital signs
- Physical Examinations

The following variables are to have their baseline value defined as latest screening result relative to Day 1:

- Medical history & demography, Height/Weight.
- Neurological Examinations
- Vital Signs/Physical Examinations with missing Day 1 values

Where Day 1 result is missing, baseline data will be defined as the latest result from C4181005 prior to enrollment, where available.

Medical history and concomitant medications ongoing from the C4181005 study will be reentered in C4181008 with the start date from when they entered into the C4181008 study.

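### The SAP's laboratory baselines disagree and all follow recifercept exposure, so a rise that began in C4181005 and persists shows as no change; Appendix 5 leaves its liver baseline undated

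*Protocol*

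**What the plan says.** **Exposure before entry.** Completion of C4181005 is an inclusion criterion (Protocol 5.1). The synopsis states: "Participants will continue to receive recifercept at the dose previously received in the Phase 2 study". Section 4.3 has the dose continuing "as assigned in C4181005 study or at the therapeutic dose once this is identified". No washout is described.

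**Laboratory schedule.** In the Schedule of Activities, the row "Blood chemistry" has its first mark at Month 3 and then one every three months. Enrollment/Day 1 has none.

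**Laboratory baselines in the SAP.** There are three statements:
- Section 2.5.2 takes the Day 1 measurement. It also says the abnormality check considers whether the baseline result lies inside or outside the reference range.
- Section 5.6.2 takes the last visit before Day 1.
- Section 2.4 gives a general fallback: "Where Day 1 result is missing, baseline data will be defined as the latest result from C4181005 prior to enrollment, where available".

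**Liver rule.** Protocol Appendix 5 makes the potential-DILI threshold depend on the child's "individual baseline values and underlying conditions". One rule covers children with normal baselines. Another covers "Preexisting AST or ALT baseline values above the normal range", with a parallel bilirubin rule that begins "TBili level increased from baseline value by an amount of at least". For potential cases confirmed on repeat testing with no other cause yet found, it states that such "cases are to be reported as SAEs, irrespective of availability of all the results". Appendix 5 does not say which measurement is the baseline.

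**The concern.** In a first-exposure study, the last value before Day 1 is also the value before the drug. In this extension it is not. Change measured from extension entry answers what happened after entry. It does not answer what has happened since recifercept started, which matters for a study whose primary objective is long-term safety. A rise that developed during C4181005 and then held steady would contribute a change near zero to the tables. It would also put the child in the abnormal-at-baseline group of the 2.5.2 check.

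The same ambiguity reaches Appendix 5. If a site read baseline as the entry value, a rise that recifercept itself had caused would lift that child's own cut-offs. Two sites could then label identical results differently. SAE frequency is part of the primary safety endpoint.

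**Working it through.** The plan gives no figure of its own to reproduce. The check has two parts, both in multiples of ULN. All patient values below are assumptions, because the documents give none.

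**1. Which value does each SAP rule yield?**

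| SAP section | Rule | What the schedule supplies |
|---|---|---|
| 2.5.2 | Day 1 measurement | No chemistry scheduled at Day 1 |
| 2.4 | If Day 1 is missing, latest C4181005 result | A C4181005 value |
| 5.6.2 | Last visit before Day 1 | A C4181005 value |

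Read alone, 2.5.2 has no scheduled chemistry value to use. If the 2.4 fallback extends to laboratory data (its lists do not name them), 2.4 and 5.6.2 will normally give the same result. They can differ if an unscheduled sample is taken on Day 1. Under any of the three, the child has already received recifercept.

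**2. Effect on the change tables.** Assume pre-recifercept AST 0.8 and last C4181005 AST 2.2.
- AST stays at 2.2 in the extension. Change from entry: 2.2 − 2.2 = 0. Change from the pre-recifercept value: 2.2 − 0.8 = +1.4.
- AST later reaches 4.0. Change from entry: 4.0 − 2.2 = +1.8. Change from the pre-recifercept value: 4.0 − 0.8 = +3.2.

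In the 2.5.2 check this child is abnormal at baseline on the entry value (2.2) and normal on the pre-recifercept value (0.8).

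**3. Effect on the Appendix 5 cut-offs.** With b the baseline AST or ALT and c the baseline TBili:
- AST/ALT cut-off = 3 if b ≤ 1; otherwise min(max(2b, 3), 8).
- TBili cut-off = 2 if c ≤ 1; otherwise min(c + 1, 3).

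| Baseline AST/ALT | Cut-off | Baseline TBili | Cut-off |
|---|---|---|---|
| ≤ 1 | 3.0 | ≤ 1 | 2.0 |
| 1.5 | 3.0 | 1.2 | 2.2 |
| 2.0 | 4.0 | 1.4 | 2.4 |
| 2.2 | 4.4 | 1.5 | 2.5 |
| 3.0 | 6.0 | ≥ 2.0 | 3.0 |
| ≥ 4.0 | 8.0 | | |

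Neither formula falls below its normal-baseline value. For a child who was normal before recifercept, using the entry value can therefore raise the cut-offs but never lower them. AST/ALT moves only when entry exceeds 1.5; TBili moves for any entry value above 1.

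**4. One child, two labels.** Assume pre-recifercept AST 0.8 and TBili 0.7; entry AST 2.2 and TBili 1.4; later AST 4.0 and TBili 2.3, confirmed on repeat, with Appendix 5's haemolysis and alkaline phosphatase conditions met and no other cause found.
- Pre-recifercept baseline: 4.0 > 3.0 and 2.3 > 2.0, so a potential DILI case, reported as an SAE.
- Entry baseline: 4.0 < 4.4 and 2.3 < 2.4, so not a potential case under the rule.

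**The case against.** The case against is strongest on Appendix 5, and most of it stands.

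- **Wording.** Appendix 5 speaks of preexisting values, which fits a value from before any recifercept. The SAP baselines are written for reporting, and nothing links them to Appendix 5. The entry-value reading is possible but not prescribed.
- **Referral.** Appendix 5 sends cases of remaining uncertainty to the sponsor. This helps, although a site that sees no ambiguity would have nothing to refer.
- **Management.** Section 7.1.1 acts on AST or ALT from 1.5 x ULN whatever the baseline, with a repeat sample for isolated elevations and possible discontinuation. Appendix 5 asks for closer monitoring above 3 x ULN. Section 7.1.1 has no bilirubin limit.
- **Recording.** Under Appendix 3, an abnormal result that needs further diagnostic testing is recorded as an AE, and medical judgment can still make it serious. The event would normally be counted; only its SAE label is in doubt.
- **Reach.** A child entering with AST or ALT above 1.5 x ULN must still be judged to have a positive risk:benefit profile. Italy excludes such children, so only TBili could shift there.
- **Tables.** Change from extension entry is a legitimate extension summary. Values are also listed, and ongoing C4181005 adverse events are carried forward.

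A reader might infer that recifercept raises liver tests, or that DILI cases will be missed. The documents support neither. Protocol 2.2.1 reports no clinically significant laboratory changes in Phase 1 (30 single-dose and 24 multiple-dose recipients) or in the first 6 Phase 2 children.

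What the objection does not remove is the SAP point. Listings let a reader find an individual child, but no planned table measures laboratory change from before recifercept.

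**Conclusion.** The point holds as a minor one. The SAP's laboratory baselines conflict in wording, one rests on a day without scheduled chemistry, and all follow recifercept exposure. A persistent rise that began in C4181005 is therefore absent from the change tables (0 rather than +1.4 x ULN in the assumed example) and is treated as a baseline abnormality in the 2.5.2 check.

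For Appendix 5 the finding is narrower: the baseline is undated. If the entry value were used, cut-offs for a child who was normal before recifercept could rise to at most 8 x ULN for AST/ALT and 3 x ULN for TBili. That bears on the SAE label, not on whether the child is looked after.

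This rests on continued dosing with no washout described (the gap between the studies is not stated) and on assumed laboratory values. How often it would matter is unknown. The details of the 2.5.2 criteria sit in sponsor reporting standards outside these documents.

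**What to change.** 1. **SAP 2.5.2 and 5.6.2.** Replace the two definitions with one extension baseline, the last C4181005 result. In addition, summarise safety laboratory data as change from the last value before the first recifercept dose in C4181005, and run the 2.5.2 baseline check against that value too.
2. **Protocol Appendix 5.** Add one sentence: baseline means the last value before the first recifercept dose in C4181005, where available.

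**Cost.** A few sentences, one extra set of tables, and possibly a few more flagged cases, which Appendix 5 already limits by repeat testing. No new blood draw is needed. The SAP already draws on C4181005 data for the height baseline (1.1.1) and the fallback (2.4). The fix relies on C4181005 having taken chemistry before its first dose. Protocol 4.2.1 says the two studies share the same assessments, but the C4181005 schedule is not shown.
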